4.5 STUDY PROCEDURES

Table 2 summarizes the procedures at each visit. The order of procedures is described in sections 4.4.1 to 4.4.7.

Table 2: Summary of procedures to be conducted at scheduled visits

Procedure	Screening	Baseline/ Dispense	Day 14	Day 42	Day 84
Informed consent	X				
Participant demographics	X				
Contact lens history	X				
Comfortable & Total CL wear time	X	×	x	×	X
Medical history and medications	Х				
Changes in medical history/medications		×	x	×	X
Compliance (Study drops & CL wear)			x	X	X
CLDEQ8	X	X	x	X	X
Symptoms via Young's criteria ⁶	X				
Subjective Ratings (Visual Analog Scales) ^{4,5}	х	х	х	х	X
HCVA (logMAR)	Х	х	х	X	X
PLNITBUT		х	х	х	Х
Lens performance (fit & wettability)	Х	X	x	х	X
Bulbar & limbal redness (Efron & K5M)	X	X	x	×	X
Lens removal	X	X	x	X	х
Tear collection		X	х	X	х
Biomicroscopy	х	х	х	х	X
Xiidra study drop application		х			
Study product dispense (drops & CL/solution)		×	x	×	х
Study product collection					х

4.5.1 CASE HISTORY

Demographics

At screening, the demographic information obtained from the participant will be age and sex.

Medical History

At screening, information will be obtained from participants about the current medication, allergies, and relevant medical conditions. At the Baseline & Dispense (V2) and Follow-up visits (V3 - V5), participants will be asked about changes in their medication or health.

Contact Lens History

Information will be obtained from the participant about the current contact lens type (lens name, brand), lens power, contact lens care solution, lens wear days, lens wear time (total and comfortable) and use of artificial tears.

4.5.2 QUESTIONNAIRES AND SUBJECTIVE RATINGS

Questionnaires

At screening; participants will be asked to assess the intensity and frequency of their CL associated dryness symptoms late in the day. Participant will be categorized as dry eye based on Young's categorization⁷ (dark grey areas in Table 3 below):

Table 3: Young's categorization for contact lens dry eye score

Categorization grid for the Contact Lens Dry Eye score.

		Never	Frequency of dryness				
			Rarely	Sometimes	Frequently	Constantly	
	Never have it – 0	No	No	No	No	No	
	Not at all intense - 1	No	No	No	No	No	
Intensity of late-day dryness	2	No	No	Marginal	Marginal	Marginal	
	3	No	No	Yes	Yes	Yes	
	4	No	No	Yes	Yes	Yes	
	Very intense – 5	No	No	Yes	Yes	Yes	

Note: Score derives from the combination of responses to frequency and intensity of dryness late in the day. Dark grey, Dry; light grey, Marginal; white, Not Dry.

Participants will complete the CLDEQ8 at every visit, reporting their experience with their habitual contact lenses in the last 2 weeks before a study visit.

Subjective ratings

Participants will be asked to complete subjective ratings of their ocular symptoms at each study visit.

Participants will be asked to rate their ocular symptoms (OU) on a 7-item visual analog scale (VAS;

Appendix 2) for a 0 (none) to 100 (worst) range; the VAS includes the following items: burning/stinging; itching; foreign body sensation; eye discomfort; eye dryness; photophobia; pain. At the screening visit, the eye dryness VAS rating needs to be >40 for a participant to be eligible.

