2 OBJECTIVES

The primary objective is to investigate whether comfort and dryness in symptomatic contact lens (CL) wearers improve after using Xiidra (lifitegrast 5.0% ophthalmic solution) for 12 weeks. In addition, this study will also evaluate whether the quantity of tear film inflammatory markers changes after use of Xiidra for 12 weeks.

The primary outcome variables for this study are subjective ratings of 'CL-related discomfort and dryness', as part of the visual analog scale (VAS) for symptom assessment, at 12 weeks compared to baseline.

Other outcome variables for this study include:

- Subjective ratings of CL-related discomfort and dryness, as part of the visual analog scale (VAS) for symptom assessment, at two and six weeks compared to baseline;
- CLDEQ-8 score at two, six and 12 weeks compared to baseline;
- Quantity of tear film inflammatory markers after 6 hours of CL wear at two, six and 12 weeks compared to baseline
 - o Inflammatory markers for 10 cytokines will be evaluated using the MSD (MesoScale Discovery) platform. The Proinflammatory Panel 1 (human) Kit will be used; it provides assay-specific components for the quantitative determination of IFN-γ, IL-1β, IL-2, IL-4, IL-6, IL-8, IL-10, IL-12p70, IL-13, and TNF-α.
- Ocular redness at two, six and 12 weeks compared to baseline;
- Non-invasive tear break-up time (pre-lens; PLNITBUT) at two, six and 12 weeks compared to baseline.

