4.2.3 INCLUSION AND EXCLUSION CRITERIA

A person is eligible for inclusion in the study if he/she:

- 1. Is at least 18 years of age and has full legal capacity to volunteer;
- 2. Has read and signed an information consent letter;
- 3. Is willing and able to follow instructions and maintain the appointment schedule;
- 4. Currently wears daily, soft, frequent replacement lenses (daily, bi-weekly or monthly disposable lenses) in both eyes, that are available in Canada, for a minimum of 5 days/week for 6 hours/day over the last month, and is willing to continue to do so during the study;
- Is a symptomatic CL wearer as determined by Eye Dryness Score^{4,5} (EDS) ≥40 at the end of the wear day AND according to the classification by Young et al⁷;
- 6. Can achieve acceptable lens fit as well as visual acuity (VA) correctable to logMAR +0.20 or better in each eye with their habitual contact lens type;
- 7. Has a history of artificial tear or rewetting drop use at least once in the last 30 days;
- 8. Is willing to use the Xiidra study drops twice a day on a daily basis (irrespective of CL wear) and to stop use of any habitual rewetting drops and/or artificial tears over the course of the 12-week treatment phase;

A person will be excluded from the study if he/she:

- 1. Is participating in any concurrent clinical or research study;
- 2. Is wearing soft CLs on an extended wear basis (i.e. overnight) or is a rigid gas permeable lens or hybrid lens wearer;
- 3. Has a known sensitivity to the investigational product or diagnostic substances (e.g. fluorescein) to be used in the study;
- 4. Has any known ocular disease and/or infection, that's either currently active* or has occurred within the previous 30 days;
- 5. Has a systemic condition that in the opinion of the investigator may affect a study outcome variable (examples may include active or uncontrolled systemic conditions such as allergies, autoimmune disease or immunodeficiency disease);
- 6. Is using any systemic or topical medications that in the opinion of the investigator may affect a study outcome variable, including but not limited to topical cyclosporine, any other topical ophthalmic medication, antihistamines, and aspirin;
- 7. Is pregnant, lactating or planning a pregnancy at the time of enrolment (by self-report);**
- 8. Has undergone refractive error surgery such as LASIK within the last 12 months;

- Has a history of yttrium-aluminium-garnet laser posterior capsulotomy within the previous 6 months,

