4.3 STUDY MATERIALS

4.3.1 CONTACT LENSES AND SOLUTIONS

Study participants will be wearing their habitual contact lens type/ brand throughout the study and will continue to use their habitual lens care if required. Participants will be instructed to wear their contact lenses for a minimum of 5 days/ week, 6 hours/day throughout the study. Participants will also be instructed to wear a new pair of lenses at each visit except for the Screening visit, at which a lens of any age (e.g. fresh daily disposable, reusable in the middle or at end of cycle).

Participants will be instructed to bring their care system (if applicable) and an unopened package of their current contact lenses to the screening visit. The specifications of the contact lenses and care system will be noted.

Participants will be supplied with contact lenses and lens care solutions (as applicable) throughout the study. Participants will also be supplied with spare contact lenses to cover the number of lenses used by the participant throughout the screening period between V1 and V2. The number of CLs to be replaced depends on the replacement modality, and will be calculated accordingly.

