4.4 SCHEDULED AND UNSCHEDULED VISITS

This study has a total of 5 study visits, including the screening visit. Participants will attend CORE for a total of 4.75 hours. A summary of all study visits is shown in Table 1 below.

Table 1: Summary of visits

Visit code	Visits	Duration
1	Screening	0.75 hrs
2	Baseline & dispense (Day 0)	1 hr
3	Day 14 Follow-up (Day 14±2)	1 hr
4	Day 42 Follow-up (Day 42±4)	1 hr
5	Day 84 Follow-up (Day 84±6 & EXIT)	1 hr
Total		4.75 hrs

Potential participants who show an interest in the study will be provided with more details about the study over the phone as well as in writing (email script). A pre-screening questionnaire (Appendix 4) will be attached to the email script sent out to participants in the CORE database or to participants expressing an interest in the study, to determine the frequency and severity of their symptoms during a typical CL wear day. If interested, potential participants can return the questionnaires to CORE, in order to determine whether they may generally be suitable for the study based on the severity of their symptoms during CL wear. Participants meeting this criterion according to the categorization by Young et al⁷ will be invited to a screening visit, where their full eligibility will be determined. Questionnaires completed prior to the consent procedure will not be included in the analysis. Volunteer participants may also be invited for a screening visit without previously completing the pre-screening questionnaire, however in order to save time and to avoid screen failures due to insufficient symptoms, completing the questionnaire prior to the screening visit is preferred.

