4.4.2 BASELINE & DISPENSE (VISIT 2; DAY 0)

Participants will attend the baseline & dispense visit after having worn a new pair of their habitual lenses for at least 6 hours prior to visit start. No habitual eye drop use is permitted on the day of this study visit. Participants are asked to bring their habitual spectacles to the visit, to be worn prior to leaving the visit after Xiidra study drop application. Baseline measurements and evaluations will be performed prior to dispense of the Xiidra study drops.

The following evaluations/procedures will be performed, in the order outlined below:

- Changes in medical history and medications;
- Comfortable lens wear and total lens wear time;
- Questionnaires
 - CLDEQ8 questionnaire;
- Subjective ratings of ocular symptoms
 - Visual analog scales, including determination of Eye Dryness Score^{4,5}
- Monocular high contrast visual acuity with habitual CL;
- Non-invasive tear break-up time over habitual CL (PLNITBUT);
- Lens performance (fit & wettability) assessment (with habitual CL);
- Bulbar & limbal redness (with habitual CLs on eye; Efron scale & K5M);
- Lens removal;
- Tear film collection;

- Slit lamp biomicroscopy using fluorescein (Safety);
- First application of Xiidra study drops
- Post-drop: Subjective ratings of symptoms and tolerability
- Monocular high contrast visual acuity with habitual spectacles or habitual CL;
- Dispense of Xiidra drops, including review of drop application process and frequency. Participants are also being reminded to not use the drops with CLs on eye;
- Dispense of habitual study lenses and care solution (if applicable) to last until the next study visit; one additional pair will be included to replace the new pair worn when attending this visit.

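### CLDEQ-8 recalls two weeks, but lens age is controlled only on the visit day, so monthly wearers may be rating lenses of different ages at baseline and follow-up

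*Combined protocol and SAP*

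**What the plan says.** Section 2 lists "CLDEQ-8 score at two, six and 12 weeks compared to baseline" among the other outcomes; the primary outcomes are VAS ratings of discomfort and dryness at 12 weeks. Section 4.5.2 sets the recall period: "Participants will complete the CLDEQ8 at every visit, reporting their experience with their habitual contact lenses in the last 2 weeks before a study visit".

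Lens age is handled in section 4.3.1: "Participants will also be instructed to wear a new pair of lenses at each visit except for the Screening visit", where a pair of any age is accepted. Section 4.4.2 has participants arrive at baseline (V2, Day 0) after wearing a new "pair of their habitual lenses for at least 6 hours prior to visit start", and sections 4.4.3 to 4.4.5 repeat this for V3, V4 and V5. Eligible wearers include those with "daily, bi-weekly or monthly disposable lenses) in both eyes" (section 4.2.3).

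At V2, participants receive enough lenses to reach the next visit, plus a pair to make up for the one opened for V2 (section 4.4.2). They may leave the follow-up visits in their habitual lenses. The protocol does not say whether the pair opened for a visit stays in use or the older pair is resumed.

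Table 1 allows V3 on Day 14 ± 2, V4 on Day 42 ± 4 and V5 on Day 84 ± 6. There is no control arm (section 4.1.2). Table 4 compares visits over time without lens age or replacement modality.

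**The concern.** The protocol standardises lens age because it could affect what is measured. That works for assessments made on the day. CLDEQ-8 describes the preceding 14 days, and nothing sets lens age in the 14 days before V2. Once the study starts, the visit schedule itself determines when a monthly wearer opens a pair, so the recalled lens age can differ systematically between baseline and each follow-up visit.

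In a single-arm study such a difference cannot be separated from an effect of the drops. At stake are the CLDEQ-8 change from baseline in monthly wearers and the shape of its time course in the repeated-measures analysis.

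A smaller, separate issue is that an early V3 visit makes the two-week recall reach back before treatment began.

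**Working it through.** The plan gives no figure on this point to reproduce, so the check computes recalled lens age directly.

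**Inputs from the documents.** Recall of 14 days (4.5.2); new pair at V2 to V5 (4.3.1); V2 on Day 0 and the visit windows (Table 1); daily, bi-weekly and monthly lenses (4.2.3).

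**Assumptions not in the documents.** A monthly pair lasts L = 28 or 30 days. The pair opened for a visit, or another fresh pair, stays in wear afterwards. Before V2, the position in the cycle is uniform over L.

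**Formula.** Lens age on day d = (d − day opened) mod L, averaged over the 14 days before the visit.

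**Monthly lenses, nominal visit days**
- V2: mean (L − 1)/2 = 13.5 (L = 28) or 14.5 (L = 30). For one wearer it can lie anywhere from 6.5 to 20.5 (L = 28) or 22.5 (L = 30).
- V3: pair opened Day 0, ages 0-13, mean 13/2 = 6.5.
- V4: pair opened Day 14, recall Days 28-41, ages 14-27, mean 41/2 = 20.5.
- V5: pair opened Day 42. With L = 28 it is replaced on Day 70, ages 0-13, mean 6.5. With L = 30 it is replaced on Day 72, ages 28, 29 and 0-11, mean (57 + 66)/14 = 8.8.

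**Permitted windows.** The same calculation was run over every combination of visit days (V3 12-16, V4 38-46, V5 78-90) and every baseline cycle position, equally weighted. For V3 on Day 12 or 13, the recall days before Day 0 were counted on the previous pair.

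| Visit | Mean age, nominal (L = 28 / 30) | Minus baseline | Mean age, windows | Minus baseline | Combinations with baseline older |
|---|---|---|---|---|---|
| V3 | 6.5 / 6.5 | −7.0 / −8.0 | 7.1 / 7.2 | −6.4 / −7.3 | 92-94% |
| V4 | 20.5 / 20.5 | +7.0 / +6.0 | 18.1 / 19.5 | +4.6 / +5.0 | 14-17% |
| V5 | 6.5 / 8.8 | −7.0 / −5.7 | 10.2 / 11.0 | −3.3 / −3.5 | about 70% |

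Week 12 is unstable because the V4-V5 gap can run from 78 − 46 = 32 to 90 − 38 = 52 days. Mean recalled age at V5 then ranges from 6.5 to 16.5 days (L = 28) or 20.2 days (L = 30).

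**Other modalities.** Daily lenses have age 0 throughout. For a 14-day cycle, any 14 consecutive days cover ages 0-13 once, so the mean is 6.5 at every nominal visit. Over the windows the only shift is about 0.3 days, at V3.

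**If the old pair is resumed after each visit.** With L = 30 the mean is 14.5 at all four visits and the difference is 0.

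**Pre-treatment recall days at V3.** max(0, 14 − visit day), counting Day 0 as treated: 2 on Day 12 (2/14 = 14%), 1 on Day 13, 0 from Day 14.

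**Effect on the score.** The documents give neither the share of monthly wearers nor any CLDEQ-8 change per day of lens age. Purely as an assumption, take a share of 25% to 100% and 0.05 to 0.2 points per day, with L = 30:
- Week 2, nominal: from 0.25 × 0.05 × 8.0 = 0.10 to 1 × 0.2 × 8.0 = 1.6 points of apparent improvement.
- Week 6, nominal: from 0.25 × 0.05 × 6.0 = 0.08 to 1 × 0.2 × 6.0 = 1.2 points of apparent worsening.
- Week 12, windows: from 0.25 × 0.05 × 3.5 = 0.04 to 1 × 0.2 × 3.5 = 0.70 points of apparent improvement.

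This range is too wide to support a claim about materiality.

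**The case against.** The strongest reply is that the shift depends on behaviour the protocol does not describe. The extra pair supplied at V2 fits a pair worn once for the visit as well as a pair kept in use, and a wearer who goes back to the older pair has no imbalance. This stands, and the point has to be conditional. Continuing with a fresh pair is still the more natural reading of a supply meant to last until the next visit, and the silence is itself a gap.

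A reader might infer that every monthly wearer rates older lenses at baseline. The documents do not support that: pre-V2 lens age is not set, and the comparison is an average over an assumed random phase. If V2 fell exactly at natural replacement, baseline would be 20.5 to 22.5 days and the older-lens shift at week 6 would vanish.

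A reader might also infer a bias towards Xiidra throughout. Week 6 goes the other way, week 12 roughly halves over the windows and can reverse, and an early V3 visit dilutes any benefit. Section 4.3.3 allows habitual rewetting drops until the day before V2 and prohibits them afterwards, which could offset part of the shift. An unmeasured opposing influence does not restore comparability, but it does rule out a claim about net direction.

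Finally, this is an open-label pilot and CLDEQ-8 is not primary. That limits the weight of the point but does not remove it, because baseline is the only comparator.

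**Conclusion.** The mismatch between a two-week recall and a visit-day lens rule is in the documents. Its consequence is conditional on a fresh pair staying in wear after each visit and a random cycle phase before V2. On those terms, monthly wearers recall lenses about 7-8 days younger than at baseline at week 2, which is the most robust result. At week 6 they recall lenses about 6-7 days older (about 5 over the windows). At week 12 the lenses are about 6-7 days younger on nominal days but only 3.3-3.5 days younger on average over the windows. Daily and bi-weekly wearers are essentially unaffected.

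The documents do not show how far this moves the score, so it would be wrong to conclude that an observed CLDEQ-8 improvement is a lens-age artefact. Nor does the point extend to the primary outcome: no two-week recall is stated for the VAS, and it is rated on a new pair at both V2 and V5.

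The early-V3 issue needs no assumption about lens use: one or two of the 14 recall days can precede the first drop.

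**What to change.** **(a) Section 4.3.1.** State which pair monthly wearers use after each visit and record the date each pair is opened. Have monthly wearers open a fresh pair 14 days before V2, and likewise before V4 and V5; the pair opened at V2 already serves V3. On nominal days every recall window then covers ages 0-13, mean 6.5. With visit windows of ± 4 and ± 6 days the ages will be similar rather than identical, so the opening dates matter. The cost is about three extra supplied pairs per monthly wearer, at least 14 days between V1 and V2, and CLDEQ-8 ratings that describe only the first half of the monthly lens cycle.

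**(b) Table 1 and section 4.4.3.** Make the V3 assessment window one-sided, no earlier than Day 14. This is a wording change with slightly less scheduling freedom.

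**(c) Section 10.1 and Table 4.** Report CLDEQ-8 change from baseline by replacement modality as a descriptive sensitivity table beside the pooled result. Lens type is already recorded at screening (section 4.5.1), so no new data are needed. With a target of 40 completers the subgroup estimates will be imprecise. Modality was not assigned, so a difference would not identify lens age as the cause. For that reason, do not add a rule that discards the pooled estimate if monthly wearers look different.

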4.5.3 VISUAL ACUITY

Visual acuity will be measured using high contrast computer-generated acuity charts. Participants will be asked to read letters that progressively decrease in size on a computer screen located at a distance of 6 meters. At the screening visit, additional trial lenses may be placed in front of the participant's eye to evaluate whether the participant's CL prescription needs to be optimized.

4.5.4 NON-INVASIVE BREAK-UP TIME (PRE-LENS)

The participant will be seated in front of a device that will project rings of light (Placido discs) onto the tear film. The participant will be asked to keep their eyes open for as long as they can and the time until the rings first begin to distort or break will be recorded. Three measurements will be taken to obtain an average value.

4.5.5 LENS PERFORMANCE

Contact lens fit

Lens fit will be assessed to ensure acceptable lens fit with a participant's habitual lenses at each of the visits.

Contact lens wettability

Contact lens wettability will be graded using 32x magnification, using a 0-4 scale, 0 = excellent wettability.

4.5.6 OCULAR REDNESS (WITH CL)

Ocular redness will be assessed for the bulbar and limbal conjunctiva, with CLs still on the eye. Assessments will include subjective grading using the EFRON Grading scale (0 to 4, 0 = normal; 0.1 increments) as well as objective measurements using the Keratograph K5M (0 to 4, 0.1 increments). To avoid potential investigator bias, subjective grades using the Efron scale will always be obtained prior to the K5M measurements.

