4.1.2 RANDOMIZATION

There is no randomization in this study. Each participant will use the same study drops, Xiidra, over the course of the 12 week study.

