4.1.3 MASKING

This is an open-label study that will not involve masking. Each participant will use the same study drops, Xiidra, over the course of the 12 week study.

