10 STATISTICAL ANALYSIS AND DATA MANAGEMENT

10.1 STATISTICAL ANALYSIS

All data will be analyzed by CORE at the University of Waterloo. Unmasked data analysis will be conducted using Statistica 13 or later. Descriptive statistics will be provided on information regarding baseline variables (age, sex, refractive error distribution, etc.). For data collected on each eye individually (e.g. biomicroscopy), results of the right eye will be reported unless a difference between right eye and left eye is found. Table 3 lists the primary and other outcome variables and anticipated statistical procedures. All data will be tested for normality of distribution using Shapiro-Wilk tests. Statistical significance will be set at 5%. Superiority testing for the primary outcome variable (i.e. VAS ratings for CL-related discomfort and dryness at 12–weeks vs baseline) will be performed, using a superiority margin of 10 units on the 100-point scale. Additional statistical testing may be applied as required.

Table 4: Statistical procedures

Variable	Analysis	Statistical test
CLDEQ-8 score,	Descriptive statistics	Mean, Standard Deviation
 VAS ratings, Pre-lens non-invasive tear breakup time (PLNITBUT), bulbar and limbal redness, tear inflammatory markers; 	Effect of time on the outcome variables (Comparison between visits)	RMANOVA/MANOVA Mauchly's test of sphericity Huynh-Feldt p values Tukey HSD post hocs Paired t-test
Safety measures (biomicroscopy, visual acuity.)	Descriptive statistics Effect of safety and exploratory variables over time	Mean, Standard Deviation RMANOVA/MANOVA Mauchly's test of sphericity Huynh-Feldt p values Tukey HSD post hocs Paired t-test

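### Ocular redness is scored by two instruments with no rule for when they disagree, and grading Efron before K5M does not keep open-label expectation out of the Efron grade

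*Combined protocol and SAP*

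**What the plan says.** Section 2 lists redness among the other outcomes in a single line: "Ocular redness at two, six and 12 weeks compared to baseline". It gives no site, instrument or eye.

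Section 4.5.6 sets out the measurement: "Ocular redness will be assessed for the bulbar and limbal conjunctiva, with CLs still on the eye". Each site is graded subjectively on the Efron scale and measured objectively with the Keratograph K5M, both from 0 to 4 in steps of 0.1. Table 2 schedules both instruments at every visit. The section's one bias safeguard concerns order: "To avoid potential investigator bias, subjective grades using the Efron scale will always be obtained prior to the K5M measurements".

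On design, section 4.1.2 states "There is no randomization in this study" and section 4.1.3 states "This is an open-label study that will not involve masking". All participants receive the same drops.

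Table 4 in section 10.1 lists bulbar and limbal redness for comparison between visits by repeated-measures ANOVA, with Tukey HSD post hocs and paired t-tests both named. It does not mention Efron or K5M in the redness entry, does not give either precedence, and does not say what follows if they disagree. Significance is set at 5%.

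**The concern.** Two gaps meet here.

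The first is about bias. Putting Efron before K5M closes one route, in which the grader sees the instrument reading and adjusts the grade towards it. Another route stays open. The grader knows that the participant is on the study drops, and nothing in the documents conceals the visit. With no concurrent control, a drift in grading between baseline and follow-up cannot cancel out. It passes in full into the change from baseline.

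The second is about precedence. An objective reading of the same sites is taken at every visit, but no text says that it prevails. If Efron falls and K5M does not, the plan leaves open which result describes redness.

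Together these allow an unmasked Efron change to be presented as an effect of treatment on redness. What is at stake is one secondary statement in the report and any use made of it in planning later studies.

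**Working it through.** The plan gives no figure for redness, so there is nothing of its own to reproduce. The calculations below show scale only.

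**Inputs from the documents.** Two sites and two instruments (section 4.5.6), so 2 × 2 = 4 scores per eye per visit. Target of 40 completers (section 4.2.2). Significance level 5% (section 10.1), taken as two-sided because the plan does not say. Four visits enter the redness comparison: baseline, Day 14, Day 42 and Day 84.

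**Assumptions, not in the documents.** SD of within-person change *s* = 0.3 to 0.5 Efron units. A mean grading shift *b* of 0.1 or 0.2 unit, that is, one or two steps of the scale. True change zero. Common correlation between the four scores from 0 to 0.7.

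**1. Effect of a grading shift alone.** The noncentrality is δ = *b* / (*s* / √40).

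- Paired t-test: 39 degrees of freedom, critical value 2.023. The probability of a significant fall is 1 − F(2.023; 39, δ), where F is the noncentral t distribution function.
- Tukey HSD over four visits: degrees of freedom (4 − 1) × (40 − 1) = 117. The critical value on the t scale is 3.686 / √2 = 2.606. The probability is 1 − F(2.606; 117, δ), taking the SD of the difference as equal for all pairs of visits.

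| Shift *b* | SD *s* | δ | Paired t | Tukey |
|---|---|---|---|---|
| 0.1 | 0.3 | 2.11 | 54% | 31% |
| 0.1 | 0.4 | 1.58 | 34% | 16% |
| 0.1 | 0.5 | 1.26 | 23% | 9% |
| 0.2 | 0.3 | 4.22 | 98% | 94% |
| 0.2 | 0.4 | 3.16 | 87% | 71% |
| 0.2 | 0.5 | 2.53 | 69% | 47% |

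**2. Choice among four scores, with no grader bias.** These are chances of at least one false change at 12 weeks against baseline.

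- Unadjusted, either direction: 1 − 0.95⁴ = 18.5% if the scores are independent. By simulation it is about 17%, 16% and 13% at correlations 0.3, 0.5 and 0.7.
- Unadjusted, favourable direction only: 1 − 0.975⁴ = 9.6% if independent, and about 6.6% at correlation 0.7. A single score gives 2.5%.
- Tukey: the two-sided level of one visit comparison is about 0.0103. Then 1 − (1 − 0.0103)⁴ = 4.1% if independent, and about 3.0% at correlation 0.7.

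The Tukey figures are low because the correction for several visits makes each single comparison stricter. It is not a correction for choosing among scores. The figures also count one eye. Section 10.1 reports the right eye unless the eyes differ, without defining a difference, and this could add candidates. Eight independent unadjusted scores would give 1 − 0.95⁸ = 33.7%.

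**The case against.** The strongest reply is that little hangs on redness. The study is a pilot, its only hypothesis concerns dryness and discomfort, and the 10-unit superiority margin applies only to the VAS ratings. Redness has no success criterion. That stands, and it limits the weight of the point. A reader might infer that some redness decision is exposed to error. The plan makes no such decision, and what remains is a risk of selective emphasis, which the text permits but does not announce. Reporting both instruments side by side would expose a change seen on Efron alone, but the plan does not commit to that.

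A reader might also infer that the plan treats redness as one undivided outcome throughout. It does not. Table 4 and the visit schedules name both sites, and the visit schedules and Table 2 name both instruments. The gap is that Table 4 names no instrument and no rule for disagreement.

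Nor should section 4.5.6 be read as claiming that the order removes every source of bias. The order works against anchoring, and section 4.1.3 is open about the absence of masking. No direction for redness is stated either, so a hoped-for reduction is an inference from the symptom hypothesis.

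Finally, the size depends on the test. Table 4 lists both Tukey post hocs and paired t-tests without saying which governs. Quoting only the paired t-test would overstate the case, so both are shown.

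**Conclusion.** The point holds as a request for clarification at low cost. Efron grades at two sites are unmasked in a study with no control. The order of assessment does not address expectation, and no text gives the objective measurement precedence.

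Under the assumed SDs, with 40 completers and no true change, a mean grading shift of 0.2 unit would be significant 69–98% of the time by paired t-test or 47–94% by Tukey. For a shift of 0.1 unit the figures are 23–54% or 9–31%. The documents give no evidence that any such shift will occur. The separate multiplicity element is modest if Tukey governs (about 3–4%) and larger if unadjusted tests do (13–19%, or about 6.6–9.6% in the favourable direction).

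The documents do not support extending this to the primary conclusion, which rests on participants' own VAS ratings. They also give no ground for preferring bulbar to limbal redness as the lead.

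**What to change.** In section 2, section 4.5.6 and Table 4, state that conclusions about redness rest on the K5M measurements. Then do one of two things:

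- have the sponsor name the lead K5M site in advance, so that a single redness score is tested at 5%; or
- report both K5M sites with a multiplicity adjustment, for example Bonferroni at 0.05 / 2 = 0.025 each.

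Label both Efron grades as supportive and descriptive, and keep the Efron-before-K5M order, which has its own use.

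The cost is wording, since K5M is already recorded at every visit. The downside is that Efron grades no longer count as evidence of effect. The change takes the grader's judgement out of the redness claim. It does not supply a control, so a K5M change would still be a before-after finding.
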